2. STUDY PROTOCOL

This was a prospective comparative clinical study to be conducted at one clinical site located in the United States. Three Nidek Mirante devices, three Optovue RTVue XR Avanti devices and one OPTOS P200DTx will be used. For agreement and precision analysis of OCT scans and agreement analysis of image quality of OCT ACA scans, each Nidek Mirante device will be paired with one of the Optovue RTVue XR Avanti devices. One device operator will be assigned to each device pair to create three distinct operator/device configurations.

For agreement analysis of SLO image quality, one OPTOS P200DTx will be included in one of three operator/device configurations.

Both eyes of normal subjects must meet all inclusion and none of the exclusion criteria in order for the subject to be enrolled in the study. Eligible subjects will be randomized to testing sequence of devices, the starting device (Nidek Mirante, Optovue RTVue XR Avanti or OPTOS P200DTx) and for the normal subject population, the study eye. For subjects in the glaucoma, retinal disease or corneal groups, the investigator will select the study eye based on presence of qualifying pathology. [REDACTED]

The Nidek Mirante, Optovue RTVue XR Avanti, and OPTOS P200DTx will be used in accordance with this clinical protocol and each device's User Manual.

Normal, glaucoma, and retinal disease subjects as well as corneal disease subjects enrolled to obtain measurements to demonstrate both agreement and precision will be randomized to the device configuration order and to the starting device within each configuration. Separate randomization schedules will be created for each subject population group (normal, glaucoma, retinal disease and corneal disease).

Corneal disease subjects enrolled to obtain only measurements to demonstrate qualitative agreement will be assessed at configuration 3 (C3) only and randomized using the next available corneal disease group randomization with C3 starting configuration to assign subject ID and starting device.

[figure not shown]
[figure not shown]
The device order will be randomly assigned as one of 2 sequences of Device (D), with D1: Test: Nidek Mirante and D2: Control: Optovue RTVue XR Avanti (OCT) and OPTOS P200DTx (SLO).

For the configurations with OPTOS P200DTx, the SLO scans for both devices will be taken after the OCT scans are completed for both devices. The SLO scans will be obtained in the same device order as for OCT.

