3. STATISTICAL ANALYSIS PLAN

Analysis of Agreement Endpoints

Analysis of the agreement study endpoints will include measurements from Nidek Mirante and the predicate device. Descriptive statistics of each agreement study endpoint will be provided by subject population for each device.

Analysis of the agreement study endpoints of the scan size and tracing HD functions will include measurements from one Nidek Mirante and be analyzed in the same fashion as detailed above.

Analysis of Precision Endpoints

Analysis of the precision study endpoints will include measurements from the Nidek Mirante and predicate device, summarizing the precision results in units measured and as a percentage of the mean across all eyes (% CV). Plots of the within-eye SD for each machine versus the within-eye mean will be provided with different symbols for the two different device types.

[REDACTED]

[REDACTED]

[REDACTED]

Analysis of the Image Quality Assessments

The number of eyes with unacceptable and acceptable image quality will be summarized and compared by device, subject population and for all subjects.

The first acceptable ACA images captured by the Mirante and Optovue RTVue XR Avanti will be compared to assess image quality.

The first acceptable SLO image captured by the Mirante and P200DTx will be compared to assess image quality.

[REDACTED]

[REDACTED]

[REDACTED]

[REDACTED]

Analysis of Safety Endpoints

Adverse events reported will be listed by subject.

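### Does the % CV for precision pool normal and diseased eyes and so hide measurement error in the diseased groups?

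*Combined protocol and SAP*

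**What the plan says.** Section 3 of the SAP, Analysis of Precision Endpoints, covers both device types and describes "summarizing the precision results in units measured and as a percentage of the mean across all eyes (% CV". It then adds a display: "Plots of the within-eye SD for each machine versus the within-eye mean will be provided with different symbols for the two different device types". Three redacted blocks come next, before the image-quality paragraph begins.

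The paragraphs on either side are explicit about population. For agreement: "Descriptive statistics of each agreement study endpoint will be provided by subject population for each device". For image quality, counts "will be summarized and compared by device, subject population and for all subjects".

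Section 2 shows who contributes precision data: "Normal, glaucoma, and retinal disease subjects as well as corneal disease subjects enrolled to obtain measurements to demonstrate both agreement and precision". It also keeps the groups apart at randomization: "Separate randomization schedules will be created for each subject population group (normal, glaucoma, retinal disease and corneal disease". No reason for the separate schedules is given.

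**The concern.** Population is named in the agreement and image-quality paragraphs but not in the precision sentence between them, and that sentence refers to all eyes. A reader may conclude that one SD is divided by one grand mean over four different kinds of eye. Such a figure would depend on the enrolment mix as well as on the device. If diseased eyes are thinner at the same SD, or noisier, good repeatability in normal eyes would mask poorer repeatability where the device is most needed. The SD-versus-mean plot would not make up for this, because as described its symbols separate device types and not populations.

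**Working it through.** **No documented figure to reproduce.** The documents give no mean, within-eye SD, group size or % CV. All inputs below are assumptions, used only to see what pooling would do if it took place.

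**Formulas.** For a diseased share w:
- the group's own % CV = 100 × SD_d / mean_d
- pooled % CV = 100 × √[(1−w)·SD_n² + w·SD_d²] / [(1−w)·mean_n + w·mean_d]

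**Equal groups (w = 1/2).**

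| Normal (mean, SD) | Diseased (mean, SD) | Pooled % CV | Diseased own % CV | Ratio |
|---|---|---|---|---|
| 100, 2 | 70, 4 | √10 / 85 = 3.72 | 4/70 = 5.71 | 0.65 |
| 100, 3 | 70, 3 | 3 / 85 = 3.53 | 3/70 = 4.29 | 0.82 |
| 100, 2 | 70, 1.4 | √2.98 / 85 = 2.03 | 1.4/70 = 2.00 | 1.02 |
| 100, 2 | 130, 2 | 2 / 115 = 1.74 | 2/130 = 1.54 | 1.13 |
| 270, 3 | 350, 9 | √45 / 310 = 2.16 | 9/350 = 2.57 | 0.84 |
| 270, 3 | 350, 6 | √22.5 / 310 = 1.53 | 6/350 = 1.71 | 0.89 |
| 270, 3 | 350, 3 | 3 / 310 = 0.97 | 3/350 = 0.86 | 1.13 |

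The direction is not fixed. In the thickened-tissue case (means 270 and 350, normal SD 3), the two values are equal when (9 + s²)/2 = s² × (310/350)². This gives s² = 9/0.569 = 15.8, so s is about 4.0. Below that SD, pooling overstates the diseased group's error; above it, pooling understates it.

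**Enrolment mix.** With normal eyes at (100, 2) and diseased eyes at (70, 4), the pooled % CV is 3.14, 3.72 and 4.33 for w = 1/3, 1/2 and 2/3, while the diseased group's own value stays at 5.71. Over the wider grid (normal 100, 2; diseased mean 70 to 130, SD 1.4 to 4; w from 1/3 to 2/3), the ratio of pooled to own % CV runs from 0.55 to 1.54.

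**Does the text say that pooling takes place?**
1. The denominator is a mean over eyes. The next sentence speaks of within-eye SD and within-eye mean. In that setting, a mean across all eyes has an ordinary technical sense: the SD is divided by the average over eyes, not by each eye's own mean. That sense holds just as well if the calculation is run once per population.
2. Where the SAP plainly means everyone combined, as in image quality, it says so alongside the by-population result. The precision sentence has no such phrase.
3. The visible precision text is evidently incomplete. It gives no variance model and does not define repeatability or reproducibility. The redacted blocks that follow are a natural place for those and for any by-population reporting.
4. Separate randomization schedules per population fit a by-population analysis at least as well as a pooled one.

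**The case for a change.** The strongest counter-argument is that the denominator is visible and unredacted. On a plain reading, all eyes means every eye contributing precision data, and the authors named population in two other paragraphs but not here. Reporting in measured units is only a partial safeguard: it avoids the denominator, but a pooled SD would still mix the groups. Tabulating by population would cost only some table rows.

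Much of this stands. The sentence does not commit to results by population, and if populations were combined the % CV could mislead in either direction. What does not stand is the step from an unqualified sentence to an established pooling rule, because the contrast with the other paragraphs treats a partly redacted paragraph as if it were complete. Using a root-mean-square of within-eye CVs, or working on the log scale, would be a different convention and would not correct an error.

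**Conclusion.** No change to the plan follows. The visible sentence leaves open whether SD and % CV are computed within each population, and the redacted text beside it may settle the matter. This is a gap that analysts fill sensibly. The design keeps the populations separate, agreement is already described by population, and each group's SD and mean can be computed from the same data at any time. The visible text attaches no acceptance limit to the % CV, so no stated decision turns on which reading applies.

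Had pooling been established, the effect could have been material: 0.55 to 1.54 times the diseased group's own % CV under the assumed inputs. That range rests wholly on assumed means, SDs and shares, and it includes overstatement, so a general claim that pooling dilutes error in diseased eyes is not supported. The conclusion rests on two points: the phrase admits a within-population reading, and text withheld by redaction is not counted as missing.
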